#### Secondary Efficacy Analyses:

- DOR will be calculated for those patients with a CR or PR from the time of first response to PD, using Kaplan-Meier methods
- The proportion of patients demonstrating DCR defined as  $CR + PR + SD \ge 8$  weeks, will also be presented along with 2-sided confidence intervals
- The proportion of patients receiving the optimal dose of duvelisib will be summarized
- PFS will be assessed using Kaplan-Meier methods from time of first treatment to PD, or death
- OS will be assessed using Kaplan-Meier methods from time of first treatment to death

#### **11.10.** Safety Analyses

Safety analyses will be performed on the Safety population, and safety endpoints will be tabulated and presented.

AEs will be coded using the Medical Dictionary for Regulatory Activities (MedDRA) for purposes of summarization. All AEs occurring during the study will be included in by-patient data listings and tabulated by MedDRA system organ class and preferred term. Adverse events will be summarized overall, by relationship and by severity. Events leading to death, SAE, and events resulting in treatment discontinuation will be listed and, if warranted by the data, tabulated.

Exposure to study drug and study drug compliance will be tabulated.

A by-patient listing of ECOG performance status data will be prepared.

The actual value and change from Baseline to each on-study evaluation will be summarized for vital sign measurements, as warranted by the data. By-patient listings of vital sign measurements will be prepared.

Individual patient laboratory parameter values and summary statistics over time will be prepared using descriptive statistics. Severity of select clinical laboratory measures will be determined using NCI CTCAE criteria and Grade 3 or 4 laboratory values will be presented in a separate patient listing.

The use of concomitant medications, coded using World Health Organization Drug Dictionary, will be included in by-patient listing.

Additional safety analyses may be performed to most clearly enumerate rates of toxicities and to further define the safety profile of duvelisib.

# 11.11. Pharmacodynamic and Biomarker Data

Pharmacodynamic and Biomarker analyses will be conducted on all or some of the Safety Population. Pharmacodynamic sample collection will only occur in the US.

Biomarkers such as gene mutation status, gene translocations, immunophenotype, functional immune assays, gene expression, and cytokines, will be evaluated with regard to baseline levels and change to baseline levels. Additional exploratory analyses identified by the Sponsor also may be performed. Listing of individual patient and summary statistics for duvelisib effects on biomarkers and graphs of changes versus time will be prepared. Biomarker effects will be summarized using descriptive statistics and associations with clinical efficacy and/or safety outcomes may be explored.

# 11.12. Pharmacokinetic Data

Pharmacokinetic analyses will be conducted on the Safety Population.

Blood samples will be taken for the analyses of duvelisib and possible metabolite(s) in plasma at the time points defined in the schedule of assessments. The relevant PK parameters will be determined using bioanalytical data. The PK data will be summarized using descriptive statistics and will be listed and summarized in tabular and/or graphical form.

# 11.13. Interim Analyses

During the Dose Optimization Phase, the ORR will be evaluated in the first 5 evaluable patients for each cohort. Enrollment may discontinue in either cohort if no CR/PR is noted in the first 5 evaluable patients.

After a sufficient number of patients from the Dose Optimization Phase are evaluable, all available data will be reviewed and an optimal dose for the Expansion Phase will be selected (Note: the optimal dose for the Expansion Phase has been selected and documented in Protocol Amendment 2, V3, 14 March 2019 – see Expansion Phase Dose Selection below and Section 1.3). The interim results of the Optimization Phase may also drive changes to the Expansion Phase of the study such as modification to the study patient population, other aspects of entry

criteria, and the inclusion of patients from geographic regions outside the US; any such changes will be documented in an amendment to the protocol. The Secura Bio study team, in collaboration with the Investigators, will make the determination of duvelisib dose for the Expansion Phase of the study based on the safety and activity data.

During the Expansion Phase, an assessment of ORR will be conducted after 40 patients have been followed for a minimum 4 months from the last patient's first dose. Enrollment in the Expansion Phase may be held if ORR as assessed by IRC is less than 20%. At that time, the efficacy data (including durability of response) will be reviewed in combination with safety and PK and upon review, the study may be fully stopped for futility.

Interim analyses may be performed at various timepoints during the Expansion Phase. The additional interim analyses should have no impact on statistical power, as the study is an open label single arm design.

# **12. ADMINISTRATIVE REQUIREMENTS**

# **12.1.** Good Clinical Practice

The study will be conducted in accordance with ICH-GCP and the appropriate regulatory requirement(s). The Investigator will be thoroughly familiar with the appropriate use of the study drug as described in the protocol and the IB.

# **12.2.** Ethical Considerations

Before implementing this study, the protocol, the proposed patient informed consent forms and any other information provided to the patients, must be reviewed and approved by a properly constituted IRB/IEC/CEC.

Any substantive change or addition to the protocol can only be made in a written protocol amendment that must be approved by the Sponsor, the IRB/IEC/CEC and the Regulatory Authority.

The study will be conducted only at sites where IRB/IEC/CEC approval has been obtained. The protocol, IB, ICF, advertisements (if applicable), written information given to the patients (including diary cards), safety updates, annual progress reports, and any revisions to these documents will be provided to the IRB/IEC by the Investigator or the Sponsor, as required by local regulations.

# **12.3.** Informed Consent

After the study has been fully explained, written informed consent will be obtained from either the patient or his/her guardian or legal representative prior to study participation. The method of obtaining and documenting the informed consent and the contents of the consent must comply with ICH-GCP and all applicable regulatory requirements. Patients who are detained by administrative or judicial order will be excluded from participating in the study.

# 12.4. Patient Confidentiality and Disclosure

The Investigator and Investigator's staff shall maintain the confidentiality of all patient records. To maintain patient privacy, all eCRFs, study drug records, reports and communications will identify the patient by initials where permitted and/or the assigned patient number. The patient's confidentiality will be maintained and will not be publicly available to the extent permitted by the applicable laws and regulations.

# 12.5. Data Collection

The Investigator is required to prepare and maintain adequate and accurate case histories designed to record all observations and other data pertinent to the study for each patient.

Secura Bio or designee will provide the study sites with secure access to and training on the electronic data capture system, sufficient to permit site personnel to enter or correct information in the eCRFs. eCRFs will be completed for each study patient. The Investigator is responsible for ensuring the accuracy, completeness, and timeliness of the data entered in the eCRF. The audit trail will indicate the user's identification information and date and time of entry and/or change.

eCRFs should be completed in a timely manner, and every effort should be made to have forms completed and up-to-date.

At the conclusion of the study, Secura Bio or a designee will retain the eCRF data and corresponding audit trails. A copy of the final archival eCRF in the form of a CD or other electronic media will be placed in the Investigator's study file.

# **12.6.** Patient Data Protection

Patients will be assigned a unique identifier during Screening. Any patient records or datasets that are transferred to the Sponsor will contain the identifier only; patient names or any information that would make the patient identifiable will not be transferred.

The patient must be informed that his/her personal study-related data will be used by the Sponsor in accordance with local data protection law. The level of disclosure must also be explained to the patient who will be required to give consent for their data to be used as described in the informed consent.

The patient must be informed that his/her medical records may be examined by Clinical Quality Assurance auditors or other authorized personnel appointed by the Sponsor, by appropriate IRB/IEC/CEC members, and by inspectors from regulatory authorities.

# 12.7. Data Quality Assurance and Monitoring

The Investigator must permit study-related monitoring, audits, IRB/IEC review, and regulatory agency inspections and provide direct access to source data documents.

Monitoring details describing strategy (e.g., risk-based initiatives in operations and quality such as Risk Management and Mitigation Strategies and Analytical Risk-Based Monitoring), methods, responsibilities, and requirements (including handling of noncompliance issues and monitoring techniques [central, remote, or on-site monitoring]) are provided in the Monitoring Plan.

The Sponsor or designee is responsible for the data management of this study, including quality checking of the data.

The Sponsor assumes accountability for actions delegated to other individuals (e.g., contract research organizations).

Study monitors will perform ongoing source data verification to confirm that data entered into the CRF by authorized site personnel are accurate, complete, and verifiable from source documents; that the safety and rights of patients are being protected; and that the study is being conducted in accordance with the currently approved protocol and any other study agreements, ICH GCP, and all applicable regulatory requirements.

Upon study completion, the monitor will arrange for a final review of the study files, after which the file should be secured by storage for the appropriate period as specified in Section 12.12 Retention of Documents.

# **12.8.** Auditing Procedures

In addition to routine monitoring Secura Bio or designee, the IRB/IEC/CEC, or Regulatory Authority may inspect the study (during the study or after its completion) to evaluate compliance with the protocol and GCP.

The Investigator agrees that representatives of the Sponsor and Regulatory Authorities will have direct access, both during and after the course of this study, to audit and review all study-relevant records.

# 12.9. Investigator Compliance

The Investigator will conduct the study in compliance with the protocol provided by Secura Bio and approved by the IRB/IEC/CEC and the appropriate regulatory authority. Modifications to the protocol will not be made without agreement of Secura Bio, the IRB/IEC/CEC and the regulatory authority, except where modification is needed to eliminate an immediate hazard to the patient. In this event, the Investigator will contact Secura Bio or designee to discuss the planned course of action. Any deviation from the protocol must be documented.

#### **12.10.** Product Complaints

If a product complaint indicating dissatisfaction regarding the study drug is received, the Investigator should contact Secura Bio or designee. A product complaint in and of itself is not an AE. If a product complaint results in an SAE, an SAE form should be completed per the defined procedure.

#### 12.11. Study Closure

Secura Bio or designee will notify the Regulatory Authorities and IRB/IEC/CECs that the study has ended.

Study participation by individual sites or the entire study may be prematurely terminated if in the opinion of the Investigator or Secura Bio there is sufficient reasonable cause. Written notification documenting the reason for study termination will be provided to the Investigator or Secura Bio by the terminating party.

Circumstances that may warrant termination include but are not limited to:

- Determination of unexpected, significant, or unacceptable risk to patients
- Failure to enter patients at an acceptable rate
- Insufficient adherence to protocol requirements
- Insufficient, incomplete, and/or unevaluable data
- Plans to modify, suspend or discontinue the development of the study drug

#### 12.12. Retention of Documents

The Investigator must maintain source documents for each patient according to ICH-GCP and applicable regulatory requirements. Records will be retained for at least 2 years after the last marketing application approval or 2 years after formal discontinuation of the clinical development of the investigational product or according to applicable regulatory requirements. If the Investigator withdraws from the responsibility of keeping the study records, custody must be transferred to a person willing to accept the responsibility and Secura Bio notified.

#### 12.13. Disclosure of Information

All information provided to the Investigator by Secura Bio, Inc. or its designee, will be kept strictly confidential. The Investigator agrees to use this information to accomplish the study and will not use it for other purposes without consent from Secura Bio. No information about this study or its progress will be provided to anyone not involved in the study other than to Secura Bio or its designees, or in confidence to the IRB, or similar committee, except if required by law.

Upon completion of the clinical study and evaluation of results by Secura Bio, the hospital or institution, and/or Investigator may publish or disclose the clinical study results pursuant to the terms contained in the applicable Clinical Study Agreement. Sponsor will comply with current regulatory requirements for disclosure and submission of study results.

The results of this study may be published or presented at scientific meetings with prior approval of the Sponsor. The Investigator agrees to submit all manuscripts or abstracts to the Sponsor before submission. This allows the Sponsor to protect proprietary information and to provide comments.

The Sponsor will comply with the requirements for publication of study results. In accordance with standard editorial and ethical practice, the Sponsor will generally support publication of multi-site studies only in their entirety and not as individual site data. In this case, a coordinating Investigator will be designated by mutual agreement between the Sponsor and the Investigators.

Authorship will be determined by mutual agreement and in line with International Committee of Medical Journal Editors authorship requirements.

# 14. **APPENDICES**

#### APPENDIX 1: CONTRACEPTION GUIDANCE

The effects of duvelisib on conception, pregnancy, and lactation are unknown. Every woman of childbearing potential (WCBP) and male patients with a partner who is a WCBP must use contraception as described below. A woman is considered to be a WCBP after menarche and until becoming postmenopausal (i.e., > 55 years and postmenopausal for at least 1 year), unless permanently sterile.

At Screening, all male and female patients of reproductive potential (i.e., not surgically sterile or female patients who are not postmenopausal) must agree to use a highly effective method of contraception (see below) for the duration of study treatment, and for at least 3 months after the last dose of duvelisib. Male patients must also refrain from donating sperm during their participation in the study and for at least 3 months after the last dose of duvelisib.

The use of contraceptive methods is not required if the male patient or the male partner (of the female patient) has a documented history of a vasectomy or if the female patient or the female partner (of the male patient) has a documented history of bilateral oophorectomy, hysterectomy, or tubal ligation, or if she is > 55 years of age and postmenopausal for at least 1 year.

See Section 10.9 for requirements for pregnancy reporting.

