- 11. Male and female patients of reproductive potential (i.e., not surgically sterile or female patients who are not postmenopausal) must be willing to use a highly effective method of contraception for the duration of study treatment and for at least 3 months after the last dose of duvelisib
- 12. Signed and dated institutional review board (IRB)/independent ethics committee (IEC)/central ethics committee (CEC)-approved informed consent form before any Screening procedures are performed

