# 9. STUDY DRUG REGIMEN

## 9.1. Dosing and Administration of Study Drug

All eligibility criteria must be met and documented prior to study drug administration. The study drug will be administered only to eligible patients under the supervision of the Investigator or identified Sub-Investigator(s).

Duvelisib is to be self-administered by patients as an oral capsule supplied by the Sponsor. Patients will receive duvelisib PO BID continuously in 28-day cycles.

On C1D1, the morning dose will be administered in the clinic. Duvelisib also will be administered in the clinic on PK sample collection days (see Table 5). An attempt should be made to enable each dose to be taken at approximately the same time of day. Missed doses outside the windows defined above or vomited doses should not be taken or repeated.

Duvelisib should be swallowed whole with a glass of water (approximately 8 ounces or 240 mL). Duvelisib may be administered without regard to meals, however, patients must avoid grapefruit and grapefruit juice while on duvelisib.

Dose reductions and interruptions for individual patients because of toxicity may be made based on the clinical judgment of the Investigator (see Section 9.4). In the event of a dose reduction, doses of less than 25 mg will utilize the 5 mg capsules.

Refer to the Pharmacy Manual for additional instructions regarding study drug administration.

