#### 9.5.3. Contraception and Pregnancy

The effects of duvelisib on conception, pregnancy, and lactation are unknown.

At Screening, male and female patients of reproductive potential (i.e., not surgically sterile or female patients who are not postmenopausal) must be willing to use a highly effective method of contraception for the duration of study treatment and for at least 3 months after the last dose of duvelisib. See Appendix 1 for Contraceptive Guidance including examples of highly effective contraceptive methods. Pregnancy testing will be performed throughout the study as shown in the Schedule of Events (Table 1 and Table 2).

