#### **Highly Effective Forms of Contraception**

Methods that can achieve a failure rate of less than 1% per year when used consistently and correctly are considered as highly effective birth control methods. Such methods include:

- combined (estrogen and progestogen containing) hormonal contraception associated with inhibition of ovulationa:
  - oral
  - intravaginal
  - transdermal
- progestogen-only hormonal contraception associated with inhibition of ovulationa:
  - oral
  - injectable
  - implantableb
- intrauterine device (IUD)b
- intrauterine hormone-releasing system (IUS)b
- bilateral tubal occlusionb
- vasectomized partnerb,c
- sexual abstinenced

a Hormonal contraception may be susceptible to interaction with the IMP, which may reduce the efficacy of the contraception method.

bThis method of contraception should preferably be used, in particular when contraception is introduced as a result of participation in the clinical study.

cVasectomized partner is a highly effective birth control method provided that partner is the sole sexual partner of the WCBP study participant and that the vasectomized partner has received medical assessment of the surgical success.

d Sexual abstinence is considered a highly effective method only if defined as refraining from heterosexual intercourse during the entire period of risk associated with the study treatments. The reliability of sexual abstinence needs to be evaluated in relation to the duration of the clinical study and the preferred and usual lifestyle of the patient.

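### Appendix 1 exempts a female patient from contraception on a record of her partner's vasectomy alone, although footnote c of the same appendix requires proof that it succeeded

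*Protocol*

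**What the plan says.** Four parts of the protocol bear on a woman of childbearing potential (WCBP) whose partner has had a vasectomy.

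- **Inclusion criterion 11 (Section 5.1).** Patients of reproductive potential "must be willing to use a highly effective method of contraception for the duration of study treatment and for at least 3 months", counted from the final dose. The criterion has no exception for a partner's vasectomy. Section 9.1 adds: "All eligibility criteria must be met and documented prior to study drug administration".
- **Section 9.5.3.** It repeats the requirement and then sends the site to the appendix: "See Appendix 1 for Contraceptive Guidance including examples of highly effective contraceptive methods".
- **Appendix 1, opening paragraphs.** Patients of reproductive potential "must agree to use a highly effective method of contraception (see below) for the duration of study treatment"; the obligation then runs on for 3 months or more. The next paragraph is a waiver: contraception "is not required if the male patient or the male partner (of the female patient) has a documented history of a vasectomy".
- **Appendix 1, list of highly effective methods.** The standard is stated first: "Methods that can achieve a failure rate of less than 1% per year when used consistently and correctly are considered as highly effective". A vasectomized partner is on the list, subject to footnote c, which accepts him provided that the "partner is the sole sexual partner of the WCBP study participant and that the vasectomized partner has received medical assessment of the surgical success".

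**The concern.** The waiver and footnote c address the same situation and set different tests. A record of a vasectomy shows that an operation took place. Footnote c treats its success as a separate matter that must be medically assessed. A site that applies the waiver literally stops there and never reaches the list that carries the footnote.

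What is at stake is fetal exposure. Section 1.4 names reproductive toxicity among the potential risks of duvelisib, and Appendix 1 states that its effects on conception and pregnancy are not known. The waiver allows a WCBP to use no other method when the protocol's own standard for relying on her partner has not been shown to be met. She could also be dosed without meeting criterion 11.

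**Working it through.** The protocol gives no figure on this point and no formula applies, so the check compares the texts.

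**Step 1: count the conditions.** The waiver sets one: a documented vasectomy. Footnote c sets two: sole sexual partner, and medical assessment of surgical success. Of those two, assessed success is absent from the waiver. The sole-partner condition is not stated there, though the reference to the patient's male partner in the singular may imply it.

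**Step 2: apply both rules to the same patient.** In each case she is a WCBP whose partner has a record of a vasectomy.

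| Partner's status | Appendix 1 waiver | Criterion 11 read with footnote c |
|---|---|---|
| Success assessed, sole partner | No contraception needed | Highly effective method in place |
| Success not assessed, sole partner | No contraception needed | Not a highly effective method; another is needed |
| Success assessed, not sole partner | Exempt if read literally | Not a highly effective method; another is needed |

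The second row is the firm contradiction. The third depends on how the singular partner is read.

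**Step 3: see whether the rules can be reconciled.** Her partner's operation does not change her own status. Criterion 11 removes a woman from its scope only if she is surgically sterile or postmenopausal. Read literally, the waiver also leaves footnote c with almost nothing to do, since any WCBP whose partner has a documented vasectomy is exempted before the method list applies. No section ranks one rule above the other.

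**Step 4: see whether pregnancy testing closes the gap.** Tests are required before the first dose, and in the Expansion Phase they are repeated monthly (Section 6.10.2, Table 2). They detect a pregnancy and do not prevent one. They also end before the contraception period does. The last scheduled test is at Safety Follow-up, 30 to 37 days after the last dose, whereas contraception is required for at least 3 months. Taking 3 months as 90 days, 90 − 37 = 53 and 90 − 30 = 60, so at least 53 to 60 days have no scheduled test. Further tests are at the investigator's discretion.

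**Step 5: gauge how many patients are involved.** The documents give no count of WCBP or of vasectomized partners. Section 4.2 plans 130-160 patients across both phases, and Section 1.1 describes PTCL as generally affecting people aged 60 and older. The number is therefore likely to be small, but it cannot be estimated from the documents.

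**The case against.** The best case for leaving the text alone is that the rest of the protocol already points the right way. Criterion 11 and Section 9.5.3 require a highly effective method and contain no partner waiver. Section 10.9 calls treatment of a WCBP without effective contraception contraindicated. A careful investigator could take footnote c, on the same subject in the same appendix, as explaining what documentation of a vasectomy must show. Criterion 11 also tests willingness, and a woman relying on her partner's vasectomy may well be willing. Finally, harm needs a chain of events: a WCBP, a partner with an unassessed and failed vasectomy, and a site that uses the waiver alone.

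Much of this stands as a limit on size. A site that reads criterion 11 with footnote c reaches the right answer, and few patients are exposed. It does not remove the conflict. Section 9.5.3 sends the reader back to the appendix where the two rules disagree, and Section 10.9 asks only for effective contraception, a lower standard than highly effective. The willingness wording means only that a WCBP could, not necessarily would, be dosed without meeting criterion 11.

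A further objection is that an unassessed vasectomy in a male patient carries the same biological uncertainty, yet his waiver is not challenged here. That is fair as a safety remark. The textual conflict, however, is confined to partners: footnote c is written for WCBP participants, and criterion 11 excludes surgically sterile men from its scope.

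**Conclusion.** The concern holds. Appendix 1 gives two answers for a WCBP whose partner has a documented vasectomy without assessed success, and the waiver's answer falls below the protocol's own standard for a highly effective method. One of footnote c's two conditions is missing from the waiver outright; the other is unstated but may be implied. The conclusion rests on the ordinary reading that a documented vasectomy records the procedure and not its result. The number affected is probably small, and efficacy, sample size and power are untouched. It is still an operative safety instruction that can be followed to the wrong result, and it should be corrected.

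**What to change.** In the waiver paragraph of Appendix 1, delete the eight words that extend the vasectomy exemption to the male partner of a female patient. The exemption would then cover only the vasectomized male patient, along with the existing exemptions for female sterilization and menopause. A partner's vasectomy would count only as a listed method under footnote c.

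If the sponsor prefers to keep the clause, it should carry footnote c's two conditions: success of the operation medically assessed, and the partner being the patient's sole sexual partner.

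Either version resolves the conflict without changes elsewhere and can go into the next amendment. It adds no visit or study procedure. The cost is that a few patients may need their partner's vasectomy verified, as footnote c already demands, or may have to add another method.
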